6.3.13.3 Statistical Methods for Secondary Objective Analyses

If the co-primary hypotheses are significant, the following secondary hypotheses will be tested in the following pre-specified order, with each hypothesis using a two-sided 5% significance level. If an endpoint fails to reach statistical significance, following hypothesis tests will not be performed.

1) Non-Inferiority of Sci-B-VacTM, 20 weeks following the second vaccination, compared to Engerix-B®, 4 weeks following the third vaccination, will be assessed using the PPS for the entire study population (i.e., adults \geq 18 years old). The non-inferiority margin is set at 5%. The null and alternative hypotheses are as follows;

Null Hypothesis: SPR(Sci-B-VacTM) –SPR(Engerix-B®) <= -5%

Alternative Hypothesis: SPR(Sci-B-VacTM) –SPR(Engerix-B®) > -5%

Statistical Analysis Plan

Non-inferiority will be assessed using the lower bound of the two-sided 95% confidence interval. If the lower bound is greater than -5%, Sci-B-VacTM 20 weeks following the second vaccination will be declared non-inferior to Engerix-B® 4 weeks following the third vaccination, and the next secondary

hypothesis will be tested.

2) Non-Inferiority of Sci-B-Vac[™] 4 weeks following the second vaccination compared to Engerix-B® 4 weeks following the third vaccination will be assessed using the PPS for the entire study population (i.e., adults ≥ 18 years old). The non-inferiority margin is set at 5%. The null and alternative hypotheses are as follows;

Null Hypothesis: SPR(Sci-B-VacTM) –SPR(Engerix-B®) <= -5%

Alternative Hypothesis: SPR(Sci-B-VacTM) –SPR(Engerix-B®) > -5%

Non-inferiority will be assessed using the lower bound of the two-sided 95% confidence interval. If the lower bound is greater than -5%, Sci-B-VacTM 4 weeks following the second vaccination will be declared non-inferior to Engerix-B® 4 weeks following the third vaccination.

The analysis for secondary endpoints will be conducted the same approach using the PPS for the non-inferiority co-primary analysis (Section 6.3.13.2). The estimated proportions and two-sided 95% CIs for Engerix-B® at Day 196 and Sci-B-VacTM at Day 56 or Sci-B-VacTM at Day 168 as well as the difference in proportions between Engerix-B® and Sci-B-VacTM [SPR(Sci-B-VacTM) – SPR(Engerix-B®)] and two-sided 95% Miettinen-Nurminen CIs will be calculated and reported. Funnel plot will be produced to investigate the impact of center.

Sensitivity analyses using the same approach outlined above will be conducted using the FAS for both secondary analyses. These analyses will be reported both with and without patients in the FAS who are seropositive at baseline. Additional sensitivity analyses will be conducted using a Logistic Regression model, to adjust for age group. Factors for treatment and age group will be included in the model.

Analyses of the above secondary endpoints will also be conducted and reported by key sub-groups using the sub-groups identified in Section 6.2.7.

6.3.13.4 Exploratory Objective Analyses

Analysis of all exploratory immunogenicity endpoints will be based on the PPS, unless otherwise indicated. Exploratory efficacy endpoints will be summarized and analyzed without adjustment for multiple comparisons.

Geometric mean concentration (GMC)

All statistical analyses will be performed on the logarithmically (base 10) transformed values.

Statistical Analysis Plan

Adjusted estimates of GMCs and their associated 95% CIs at Day 28, Day 56, Day 168, Day 196 and Day 336 will each be determined using an analysis of covariance (ANCOVA) model with factors for treatment, age group, and a covariate for the log transformed pre-vaccination (baseline) titer. Antibody GMCs, associated standard errors, two-sided 95% CIs and median, minimum, and maximum titer values will be determined and presented by treatment group. The median, minimum, and maximum values will be reported on the actual titer values, rather than the log scale. The difference in GMCs between the two treatment groups, and associated two-sided 95% CIs will also be presented. Imputation methods will not be used.

The above analyses will be conducted and reported for all subjects age \geq 18 years old and for subjects age \geq 45 years old. Analyses of GMC in both age cohorts will also be reported by sub-group using the sub-groups identified in Section 6.2.7. Sub-group analyses will include additional factors in the model, a factor for the sub-group of interest and the interaction between the sub-group and treatment.

Sample SAS code for ANCOVA model:

```
PROC MIXED;
CLASS treatment agegrp;
MODEL log(var) = treatment agegrp log(baseline of var);

/* var = anti-HB titer GMC */
LSMEANS treatment / DIFF CL ALPHA=0.05;
ODS OUTPUT LSMEANS=ls_means Diffs=diff;

QUIT;
RUN;
```

Sample SAS code for ANCOVA model for sub-group analyses:

```
PROC MIXED;
CLASS treatment agegrp;
MODEL log(var) = treatment agegrp log(baseline of var) subgroup subgroup*treatment;
LSMEANS treatment / DIFF CL ALPHA=0.05;
ODS OUTPUT LSMEANS=ls_means Diffs=diff;
QUIT;
RUN;
```

where var represent the anti-HBs titer, treatment represents treatment group, agegrp represents age group (18 - 44 years, 45 - 64 years, >=65 years) and subgroup represents subgroup defined in Section 6.2.7.

Binary data (e.g. proportion of subjects with anti-HBs levels ≥ 100 mIU/mL and proportions of subjects achieving seroprotection, please see Section 1.3 for all binary data interested) will be summarized using frequency counts and percentages, by time point. Data from all centers will be pooled for these analyses. The difference in proportions and two-sided 95% CIs, calculated using the Miettinen and Nurminen

Statistical Analysis Plan

method, will be reported. Additional sensitivity analyses will be conducted using a Logistic Regression model, to adjust for age group. Factors for treatment and age group will be included in the model.

• Sample SAS code for the analysis of binary data:

```
PROC FREQ; * specify and sub-select data set as applicable;
BY visit;
TABLES trt*seroprotection/riskdiff (cl=mn); * numerical 0/1-scores identify 'event';
RUN;
```

• Sample SAS code for the analysis of binary data using logistic regression:

```
PROC LOGISTIC; * specify and sub-select data set as applicable;
CLASS trt agegrp;
MODEL seroprotection = trt + agegrp * numerical 0/1-scores identify 'event';
LSMEANS trt /diff;
OUTPUT lsmeans=lsmeans diffs=diffs;
RUN:
```

• Sample SAS code for the subgroup analysis of binary data:

```
PROC FREQ; * specify and sub-select data set as applicable;
BY visit;
TABLES subgroup*trt*seroprotection/riskdiff (cl=mn); * numerical 0/1-scores identify 'event';
RUN;
```

where seroprotection represent the binary event, trt represents treatment group, agegrp represents age group (18 - 44 years, 45 - 64 years, >=65 years) and subgroup represents subgroup defined in Section 6.2.7.

The above analyses will be conducted and reported for all subjects \geq 18 years old and for subjects \geq 45 years old. Analyses of binary data in both age cohorts will also be reported by sub-group using the subgroups identified in Section 6.2.7.

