		6.3.14.6 Physical Examination	
7.	REFERENCES		40

Statistical Analysis Plan

ABBREVIATION AND ACRONYM LIST

Abbreviation / Acronym	Definition / Expansion					
AE	Adverse event					
ANCOVA	Analysis of covariance					
BLQ	Below the lower limit of quantification					
BMI	Body Mass Index					
Bpm	Beats per minute					
CI	Confidence interval					
CSP	Clinical Study Protocol					
CSR	Clinical Study Report					
CVID	Common variable immune deficiency					
DBP	Diastolic blood pressure					
eCRF	Electronic Case Report Form					
FDA	Food and Drug Administration					
FAS	Full analysis set					
GMC	Geometric mean concentration	Geometric mean concentration				
HBsAg	Hepatitis B surface antigen					
HIV	Human immunodeficiency virus					
HR	Heart rate					
IP	Investigational Product					
ITT	Intent-to-Treat					
IWRS	Interactive web response system					
LQ	Limit of quantification					
MCAR	Missing completely at random					
MedDRA	Medical Dictionary for Regulatory Activities					
NK	Not known					
NOCI	New onset of chronic illness					
PD	Protocol deviation					
PPS	Per Protocol Set					
SAE	Serious adverse event					
SAP	Statistical Analysis Plan					
SBP	Systolic blood pressure					
SD	Standard deviation or single dose					
VBI Vaccines Inc.		Final 4.0				

VBI Vaccines Inc. Sci-B-Vac-001

Statistical Analysis Plan

Abbreviation / Acronym	Definition / Expansion
SE	Standard error of the mean
SSA	Sub-study Analysis Set
SOC	System Organ Class
SPR	Seroprotection rate
SUSAR	Suspected unexpected serious adverse reactions
TEAE	Treatment-emergent adverse event
TLF	Tables, Listings and Figures
VBI	VBI Vaccines Inc
WHO-DD	World Health Organisation - Drug Dictionary

PAREXEL International Statistical Analysis Plan

STATISTICAL ANALYSIS PLAN

The Statistical Analysis Plan (SAP) details the statistical methodology to be used in analyzing study data and outlines the statistical programming specifications for the Tables, Listings and Figures (TLFs). It describes the variables and populations, anticipated data transformations and manipulations and other details of the analyses not provided in the Clinical Study Protocol (CSP). The plan for exploratory analyses of antibody responses against Pre-S1 and Pre-S2 and cell-mediated immunity directed against HBs data collected during this study will be detailed in a separate SAP and is outside the scope of this SAP. These analyses will be reported as an addendum to the main Clinical Study Report (CSR).

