1.3 Exploratory Objectives

- To compare the geometric mean concentration (GMC) of anti-HBs 4 weeks after receiving the first vaccination, the second vaccination and the third vaccination, 20 weeks after receiving the second vaccination (just prior to receiving the third vaccination), and 24 weeks after receiving the third vaccination, of Sci-B-VacTM or Engerix-B®.
- To compare the SPR observed 4 weeks after receiving the first vaccination and second vaccination, 20 weeks after receiving the second vaccination (just prior to receiving the third vaccination), and 24 weeks after receiving the third vaccination, of Sci-B-VacTM or Engerix-B® on Study Days 28, 56, 168 and 336.
- To compare the proportion of subjects who achieve anti-HBs levels ≥ 100 mIU/mL, as a measure of an especially robust immune response, 4 weeks after each vaccination with either Sci-B-VacTM or Engerix-B®, on Study Days 28, 56, and 196, and on Study Days 168 and 336.
- To compare the rate of non-response 4 weeks after receiving the third vaccination with Sci-B-Vac[™] or Engerix-B®.
- To assess the antibody responses against Pre-S1 and Pre-S2 at baseline, 4 weeks after each injection with Sci-B-VacTM or Engerix-B® and on Study Days 168 and 336.
- To compare SPR, GMC and rate of non-response in subgroups of interest (e.g. BMI>30) 4 weeks after receiving the third vaccination with Sci-B-VacTM or Engerix-B®.
- To compare clinical laboratory parameters relative to baseline 1 week after each vaccination with Sci-B-VacTMor Engerix-B® in a subset of subjects (at least 10% of the total number of subjects enrolled to the trial).
- To compare the boost, relative to baseline, of cell-mediated immune response against HBs, 1 week after receiving each vaccination with either Sci-B-VacTM or Engerix-B® (in a small subset of subjects recruited to an optional sub study at select sites (~50-75 subjects/treatment arm)).

Statistical Analysis Plan

[figure not shown]

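### The sample code for the exploratory sub-group GMC model contradicts the SAP text: it does not treat the sub-group as a factor and requests no estimate by sub-group level

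*SAP*

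**What the plan says.** SAP 1.3 lists as an exploratory objective "To compare SPR, GMC and rate of non-response in subgroups of interest". SAP 6.3.13.4 then says that the GMC analyses will be reported by sub-group, for all adults and for those aged 45 and over. The ANCOVA is to gain "a factor for the sub-group of interest and the interaction between the sub-group and treatment". Protocol 9.7 says the same.

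The code that follows is headed "Sample SAS code for ANCOVA model for sub-group analyses". Its three working lines are:

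- "CLASS treatment agegrp"
- "MODEL log(var) = treatment agegrp log(baseline of var) subgroup subgroup*treatment"
- "LSMEANS treatment / DIFF CL ALPHA=0.05"

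The first and third lines are the same as in the main (non-sub-group) ANCOVA code. Only the MODEL line has changed, by the added terms "subgroup subgroup*treatment". SAP 6.2.7 lists 11 sub-groups. The SAP's introduction says that the document "outlines the statistical programming specifications for the Tables, Listings and Figures".

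**The concern.** The text promises a categorical sub-group effect and results by sub-group. The code delivers neither, and nothing else in the SAP says how a sub-group GMC, its confidence interval or a sub-group ratio is to be obtained. A programmer who keeps the CLASS and LSMEANS lines would fill each GMC sub-group table with a contrast averaged over the sub-group. One who notices the conflict must choose the estimates unaided, either within-level contrasts from the interaction model or separate fits. Protocol 1.4 makes response in older, diabetic, obese and smoking adults part of the rationale for the trial, so readers will look at these tables.

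**Working it through.** The plan gives no figure to reproduce here. The check is of the code, line by line, followed by an illustration.

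**1. CLASS.** In PROC MIXED a model variable that is not in CLASS is a continuous covariate and must be numeric. Two outcomes follow:

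- Numeric coding: the sub-group takes one slope and one slope-by-treatment term, 2 df whatever the number of levels. A factor with k levels needs (k − 1) + (k − 1) df. For k = 2 that is 2, so the fit is identical. For k = 3 it is 4, and for k = 5 it is 8.
- Character coding: the step stops with an error.

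**2. Which sub-groups are affected (SAP 6.2.7).**

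| Levels | Sub-groups | Effect of the CLASS omission if coded numerically |
|---|---|---|
| 2 | gender, BMI, diabetes, non-study vaccines, ethnicity | none; same fit |
| 3 | smoking, alcohol, race, country/region | linear score |
| 5 | age category | linear score |
| 3 | age group | already in CLASS as `agegrp`; the term is duplicated |

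That is 5 + 4 + 1 + 1 = 11 sub-groups, of which 4 + 1 = 5 would be forced onto a linear score. Race and region have no natural order, so a linear score has no meaning for them.

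**3. LSMEANS.** The request is for the treatment effect alone, with no sub-group-by-treatment means and no other estimate by level. With a numeric sub-group s, the single log10 difference is b(treatment) + b(interaction) × mean(s). With s in CLASS it is the equally weighted average of the level-specific differences. Either way there is one contrast, and this applies to all 11 sub-groups.

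**4. Illustration.** Both models were fitted to simulated log10 titers for the planned 1,564 subjects, with age strata at the planned 20/40/40%. The rest is assumed and does not come from the documents: residual SD 0.9 log10; BMI split 63/37 with true ratios 3.98 and 10.0; smoking split 15/30/55 with true ratios 10.0, 2.51 and 5.01. Estimates differ from the true ratios through sampling error in one simulated data set.

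| | BMI (2 levels) | Smoking (3 levels) |
|---|---|---|
| Code as printed, numeric sub-group: the one ratio output | 6.86 (at mean code 0.366) | 4.70 (at mean code 2.424) |
| Ratios by level implied by that fit, not output | 5.03, 11.73 | 5.67, 4.97, 4.36 |
| Sub-group in CLASS, contrasts by level | 5.03, 11.73 | 14.04, 2.04, 5.42 |
| Sub-group in CLASS, treatment means only | 7.68 | 5.37 |
| Model df, printed code vs factor | 6 vs 6 | 6 vs 8 |

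For BMI the arithmetic can be followed by hand: log10(5.03) = 0.702 and log10(11.73) = 1.069, so the contrast at the mean code is 0.702 + 0.366 × (1.069 − 0.702) = 0.836, and 10^0.836 ≈ 6.86. The last ratio row is the geometric mean: √(5.03 × 11.73) = 7.68 and (14.04 × 2.04 × 5.42)^(1/3) = 5.37. Adding the sub-group to CLASS therefore does not by itself give results by level; both lines must change.

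**5. Comparison within the SAP.** The binary sub-group code in 6.3.13.2 and 6.3.13.4 stratifies the table by sub-group and so returns one difference per level. Only the GMC code fails to do so.

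**The case against.** The strongest reply is that the method is in the prose and the code is only a sample. The prose calls the sub-group a factor, reserves the word covariate for baseline titer, and says that results are reported by sub-group. The code cannot run as printed anyway: `subgroup` is a placeholder, the baseline term is not valid SAS, and the text asks for base-10 logs where the code writes `log`. A programmer must rewrite it and would be guided by the text. That stands, and it limits the point to a conflict between code and text. It does not remove the point, because the prose does not name the estimates and the code, where it does, names the wrong ones.

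Stronger readings are tempting, and the documents do not support them:

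- A reader might infer that the SAP's stated method omits sub-group results. The prose in SAP 6.3.13.4 and Protocol 9.7 says otherwise.
- A reader might infer that every GMC sub-group table would come from a mis-specified model. For the five two-level sub-groups a numeric code gives the same fit as a factor; only the LSMEANS request is at fault. Age group is already in CLASS as `agegrp`.
- A reader might infer that a linear trend is certain. The SAP fixes no numeric coding for these variables, and character coding would fail visibly.
- A reader might infer that `agegrp` should also be dropped for age category. These are different variables: the 40–49 band straddles the 45-year cut and the 60–69 band straddles the 65-year cut. Dropping it would remove an adjustment that the plan specifies, so that is a modelling preference and not a correction.

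**Conclusion.** The sample code is wrong as written when set against the SAP's and protocol's own text; severity is low. The LSMEANS request fails for all 11 sub-groups, whatever the coding. The CLASS omission distorts the fit for five of them (age category, smoking, alcohol, race, region) if they are coded numerically, and stops the program if they are character variables. The simulated ratios show the mechanism only; they depend on the assumed SD, splits and effects and predict nothing about this trial.

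The reach is limited to the exploratory GMC sub-group tables, which the SAP already analyses without multiplicity adjustment. The co-primary and secondary seroprotection analyses, the main GMC ANCOVA and the binary sub-group analyses do not use this code.

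**What to change.** In the sub-group code of SAP 6.3.13.4:

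1. Change the class line to `CLASS treatment agegrp subgroup`.
2. Request `LSMEANS subgroup*treatment` with differences and 95% confidence limits, and report the treatment difference within each sub-group level, back-transformed to a GMC ratio with its interval. Use the base-10 scale that the text specifies.
3. When the sub-group is the three-level age group itself, enter it once as `agegrp` with its interaction with treatment. Keep `agegrp` for every other sub-group, including age category, unless the sponsor decides otherwise and says so.

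The cost is two lines of SAP code and one sentence. No data collection, sample size or confirmatory analysis changes.

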6.3.14 Safety Analysis

Analysis for laboratory variables will be based on SSA 1. The analysis of the rest of safety variables will be based on the Safety Set.

6.3.14.1 Completer Analysis on Solicited Adverse Events

The safety completeness analysis on solicited adverse events aims to identify subjects who completed diary cards and/or remained in clinic for at least 30 minutes post vaccination, irrespective of severity. The analysis will show the number of subjects with valid data by solicited adverse event and time point. Valid data in the context of the safety completeness analysis are all data entered in the diary card and/or 30 minutes post each vaccination assessment (including implausible values) except "Not done/unknown".

Statistical Analysis Plan

Three summaries will be produced:

- 1. The frequencies of subjects who provide diary cards by vaccine group.
- 2. For each type of solicited adverse event (local, systemic, other) the frequencies of subjects with valid data by vaccine group, aggregated over time points and intervals: 0-30 min (clinic), >30 min Day 1 (diary), Day 2 7 (diary) where the Day 1 is the date of each vaccination. The Day value is incremented by 1 for each date following the date of the vaccination.
- 3. For each solicited adverse event, the frequencies of subjects with valid data by vaccine group aggregated over time points and intervals: 0-30 min (clinic), >30 min Day 1 (diary), Day 2 7 (diary) where the Day 1 is the date of each vaccination. The Day value is incremented by 1 for each date following the date of the vaccination.

For the corresponding percentages, the denominator will be the respective numbers of exposed subjects, i.e., subjects who received a vaccination, irrespective of whether a diary card was present or not. All analyses will be based on the Safety Set (i.e. 'as treated').

6.3.14.2 Solicited Local, Systemic and Other Adverse Events

The following solicited local and systemic adverse events as well as solicited other adverse events will be collected. The grading of severity will be graded according to the FDA Guidance for Industry Toxicity Grading Scale for Healthy Adult and Adolescent Volunteers Enrolled in Preventive Vaccine Clinical Trials (2007) – also see protocol Appendix 3.

Solicited local adverse events:

- Redness/erythema
- Pain
- Swelling/edema
- Tenderness
- Pruritus

Injection site reactions grading				
	Grade 1	Grade 2	Grade 3	Grade 4
Pain (pain without touching)	Does not interfere with activity	Repeated use of non-narcotic pain reliever	Any use of narcotic pain reliever or prevents daily activity	Emergency room (ER) visit or hospitalization

PAREXEL International Statistical Analysis Plan

Tenderness (pain when area is touched)	Mild discomfort to touch	> 24 hours or interferes with activity Discomfort with movement	Significant discomfort at rest	ER visit or hospitalization
Pruritus associated with injection See also Skin: Pruritus (itching - no skin lesions)	Itching localized to injection site AND Relieved spontaneously or with < 48 hours treatment	Itching beyond the injection site but not generalized OR Itching localized to injection Site requiring ≥ 48 hours treatment	Generalized itching causing inability to perform usual social & functional activities	NA
Erythema/Redness*	2.5 – 5 cm	5.1 – 10 cm	> 10 cm	Necrosis or exfoliative dermatitis
Induration/Swelling**	2.5 – 5 cm and does not interfere with activity	5.1 – 10 cm or interferes with activity	> 10 cm or prevents daily activity	Necrosis

^{*}In addition to grading the measured local reaction at the greatest single diameter, the measurement should be recorded as a continuous variable.

Solicited systemic adverse events:

- Nausea/vomiting
- Diarrhea
- Headache
- Fatigue
- Myalgia

The grading of systemic adverse events will be as follows:

^{**} Induration/Swelling should be evaluated and graded using the functional scale as well as the actual measurement.

Statistical Analysis Plan

Systemic	Mild	Moderate	Severe	Potentially Life
(General)	(Grade 1)	(Grade 2)	(Grade 3)	Threatening
				(Grade 4)
Nausea/vomiting	No interference	Some	Prevents daily	ER visit or
	with activity or 1	interference with	activity, requires	hospitalization for
	- 2 episodes/24	activity or > 2	outpatient IV	hypotensive shock
	hours	episodes/24	hydration	
		hours		
Diarrhea	2 - 3 loose stools	4 - 5 stools or	6 or more	ER visit or
	or < 400 g/24	400 - 800 g/24	watery stools or	hospitalization
	hours	hours	> 800g/24 hours	
			or requires	
			outpatient IV	
			hydration	
Headache	No interference	Repeated use of	Significant; any	ER visit or
	with activity	non-narcotic	use of narcotic	hospitalization
		pain reliever >	pain reliever or	
		24 hours or some	prevents daily	
		interference with	activity	
		activity		
Fatigue	No interference	Some	Significant;	ER visit or
	with activity	interference with	prevents daily	hospitalization
		activity	activity	
Myalgia	No interference	Some	Significant;	ER visit or
	with activity	interference with	prevents daily	hospitalization
		activity	activity	

Solicited other adverse events:

- Fever
- Tachycardia beats per minute (0-30 min only)
- Bradycardia beats per minute (0-30 min only)
- Hypertension (0-30 min only)
- Hypotension (0-30 min only)
- Respiratory rate (0-30 min only)

The grading will be as follows:

Vital Signs *	Mild (Grade 1)	Moderate (Grade 2)	Severe (Grade 3)	Potentially Life Threatening
				(Grade 4)
Fever (°C) **	38.0 - 38.4	38.5 - 38.9	1. 39.0 – 40	> 40
(°F) *	00.4 - 101.1	101.2 - 102.0	2. 102.1 – 104	> 104

Statistical Analysis Plan

Tachycardia - beats per minute	101 – 115	116 – 130	> 130	ER visit or hospitalization for arrhythmia
Bradycardia - beats per minute***	50 – 54	45 – 49	< 45	ER visit or hospitalization for arrhythmia
Hypertension (systolic) - mm Hg	141 – 150	151 – 155	> 155	ER visit or hospitalization for malignant hypertension
Hypertension (diastolic) - mm Hg	91 – 95	96 – 100	> 100	ER visit or hospitalization for malignant hypertension
Hypotension (systolic) – mm Hg	85 – 89	80 – 84	< 80	ER visit or hospitalization for hypotensive shock
Respiratory Rate – breaths per minute	17 – 20	21 – 25	> 25	Intubation

Subject should be at rest for all vital sign measurements.

All solicited AEs will be summarized according to defined severity grading scales. Frequencies and percentages of subjects experiencing each AE will be presented by treatment group for each symptom overall, and by treatment group and severity for each age group and by time point (i.e., after each vaccination).

